Statistical Analysis Plan for University of Washington School of Medicine,

Department of Rehabilitation Medicine study:

Efficacy and mechanism of a community wellness promotion program for middle-aged adults living
with long-term physical disability

PI: [name], PhD

NCT 03653390

UW IRB STUDY00007984

Initial IRB Approval: April 11, 2018

Document Last Updated: October 26, 2023

Statistical Analysis Plan

Design overview:

- 3-arm, randomized controlled trial
 - Arm 1: Enhance Wellness for Disability (8 sessions)
 - Arm 2: Health education (8 sessions of the CDC's "Keys to Healthy Aging")
 - Arm 3: Treatment as usual (TAU)
 - 6-month intervention period across 3 groups
 - 12-month follow-up across 3 groups

Assessment timeline:

- Patient reported outcomes collected at baseline (pre-randomization), and at 3, 6 and 12 months post-randomization
- GPS outcomes collected at baseline (pre-randomization) and at 12-month follow-up

Primary outcome variable:

1. Change in ability to participate in social roles and activities
 - Measured via the PROMIS Ability to Participate in Social Roles and Activities 8-item short form
 - Patient reported outcome
 - Results recorded as a t score

Secondary outcome variables (patient reported):

1. Change in satisfaction with social role participation
 - Measured via the PROMIS Satisfaction with Social Roles and Activities 8-item short form
 - Results recorded as a t score

2. Change in disease management self-efficacy
 - Measured via the University of Washington Self-Efficacy Scale, 6 item short form
 - Results recorded as a t score
3. Change in interference due to pain
 - Measured via the PROMIS-29 Profile, v. 2.1 pain interference subscale (4 items)
 - Results recorded as a t score
4. Change in interference due to fatigue
 - Measured via the PROMIS-29 Profile, v. 2.1 fatigue subscale (4 items)
 - Results recorded as a t score
5. Change in psychological resilience
 - Measured via the Connor-Davidson Resilience Scale, 10-item short form
 - Scores range from 0-40

Secondary outcome variables (GPS and travel log based):

1. Change in number of trips outside the home
 - Mean average per day
2. Change in radius of gyration
 - Results recorded in meters
3. Change in number of trips outside the home containing “social” elements
 - Based on integration of GPS and travel log report
4. Change in time of trips spent in activities outside of the home containing “social” elements
 - Results recorded in minutes
 - Based on integration of GPS and travel log report

Statistical Approach:

All analyses will follow an intent-to-treat approach.

Summary statistics (means, standard deviations, counts, and percentages), stratified by treatment assignment, were used to describe the study sample. ANOVAs were used as an omnibus test to determine if there were any differences in the change scores between treatment groups for each of the primary and secondary outcomes. If the omnibus test was significant, a post-hoc Tukey's honest significant difference tests were used to assess pairwise differences between treatment groups. A two-sided significant level of 0.05 was used to determine if differences were statistically significant. As there was only one primary outcome, no adjustment for multiple comparisons was used. Furthermore, Tukey's HSD test inherently controls the type I error rate for the pairwise comparisons.

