GROUP 3: Treatment as Usual (TAU) To establish a baseline comparison for treatment effects, participants in the TAU arm will not receive contact with a study social worker, will not receive education or fact sheet information, and will be asked to continue with their lives as they normally would. Similar to groups 1 and 2, TAU participants will complete the self-report surveys as described below.

Additional study information:

Outcome Data (GPS/diary): To objectively measure community activity and participation behavior, we will collect a combination of Global Position System (GPS) data, in conjunction with daily self-report travel diaries from a sub-set of participants (**Appendix 27, 38**).

Of the 600 individuals enrolled in the study, a subset of participants (N=100 per arm; 300 total) will be invited to a one week GPS/diary study component at two time points (at baseline and again at the 12-month assessment). Participants will be mailed a cover instruction letter, along with the portable GPS data logger (such as, QStartz BT Q1000XT GPS logger), 1 weeks' worth of paper daily travel diaries (**Appendix 27**), and an additional GPS letter with notes for completing the week of GPS data logging (**Appendix 30**). Participants will also be given the option of completing the Travel Log electronically. Participants who wish to complete the travel log electronically will be emailed an excel version of the travel log (**Appendix 38**) in addition to the paper version.

- The GPS device is small (72 x 47 x 20mm; 64.g) and can be attached with Velcro to a belt or wheelchair, or can be placed in a pocket, purse, backpack, etc. This portable device works up to 24 hours on a single charge when set at a 15 sec epoch acquisition. Participants will be provided with a charger and instructed to charge the device nightly, power them on in the morning, wear them during waking hours, and remove them at bed time. Participants will be told to go about their daily routine as they normally would.

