- The diaries used for this study modeled after the National Household Travel Survey instrument (**Appendix 27, 38**); we will collect information about each place the participant has visited throughout the day, including travel mode of arrival and purpose of visit (e.g., socializing, shopping, etc). Although electronic diaries might be more efficient for data processing (i.e., no need for transcription), not all participants in this study will have reliable daily internet access, making pen-and-paper a more reliable method. Any participants who are not able to complete pen-and-paper diaries will be given the option to provide diary information electronically using an emailed excel file (**Appendix 38**) or verbally over the telephone each day to research staff.

Participants are instructed to contact research staff when they receive their gps in the mail to review the instructions for wearing the device and completing the diary. Participants will be contacted again 3 days later to answer any additional questions and ensure compliance.

Participants will be provided with postage-paid envelopes to return materials to a study-specific address. Research staff will then review the data for completeness and will re-contact participants as needed for additional information, or in the case of the lack of useable GPS data, for device re-wearing.

Outcomes for the proposed GPS analyses will be: (1) total number of trips outside the home; (2) total number of minutes spent outside the home; (3) total “travel path length” (calculated as the summed distance between GPS points included in trips); (4) activity space, quantified as radius of gyration¹³¹; and (5) number of activity events occurring outside the home in each of 6 categories, as previously identified in other studies of GPS measured participation: shopping (daily or recreational), social/leisure (visiting friends or doing hobbies), “bring or get” activities (errands, such as getting a package from the post office), personal care (including medical care), and other. Use of the travel diary will be important in identifying specific places and activities associated with non-home locations recorded with the GPS. For example, an individual may go to a library, and the GPS will show this, but without the travel diary the investigators will not know if this was to get a book, to meet friends, or to use the internet.

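### Radius of gyration is tested by ANOVA on change in meters, with no baseline covariate or robust method, which loses substantial power if the measure is strongly right-skewed

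*SAP*

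**What the plan says.** The SAP, under Secondary outcome variables (GPS and travel log based), item 2, names "Change in radius of gyration" and adds "Results recorded in meters". Under Statistical Approach it tests "differences in the change scores between treatment groups for each of the primary and secondary outcomes" by one-way ANOVA. Pairwise comparison is conditional: "If the omnibus test was significant, a post-hoc Tukey's honest significant difference tests were used". The level is 0.05, two-sided.

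Protocol section 5.1, Outcome Data (GPS/diary), lists the measure as "activity space, quantified as radius of gyration". It comes from one recorded week at baseline and one at 12 months. On numbers, the section says that "a subset of participants (N=100 per arm; 300 total) will be invited to a one week GPS/diary study component".

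Neither document mentions a transformation, a rank-based or robust method, a rule for long trips or homebound weeks, or a baseline-adjusted model for this outcome. Neither gives its SD, distribution, expected effect or power. That the analysis is on untransformed values is inferred from the unit, the change score and this silence; the SAP does not say so outright.

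**The concern.** Radius of gyration is a root-mean-square distance, so a single far trip can set a person's value for the week. A difference of two such values in meters gives most of the weight to the few people who travelled far in one week and not in the other. It also treats a gain of 5 km as the same change for someone who starts at 1 km as for someone who starts at 50 km. One week per time point offers little averaging.

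A real increase in activity space from the intervention could therefore be hidden by the variance from a handful of travellers. This is one of four GPS-based outcomes, measured in about 100 people per arm, so there is little power to spare.

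**Working it through.** **Inputs from the documents.** Three arms; 100 per arm invited; baseline and 12 months; ANOVA on change; alpha 0.05. The plan states no power for this outcome, so there is no figure to reproduce.

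**Assumed inputs, because the documents give none.** Lognormal values with log-SD s from 0.25 to 1.5; correlation ρ between baseline and 12 months on the log scale of 0.3, 0.5 or 0.7; an effect in one arm only.

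**Step 1: one long trip.** If a share p of recorded time is spent at distance D and the rest near home, radius of gyration is about D × √(p(1−p)). One day in seven at an illustrative 300 km gives 300 × √(1/7 × 6/7) = 300 × 0.350 = 105 km, almost regardless of the other six days.

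**Step 2: who carries the variance.** With ρ = 0.5, the most extreme 5% of people (15 of 300) account for 42% of the raw-change variance at log-SD 0.5, 68% at 1.0 and 86% at 1.5.

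**Step 3: power of the planned test.** The SD of log change is s√(2(1−ρ)). For one arm shifted by d on the log scale, the noncentrality is λ = n × (2/3) × d²/SD². The effect was set so that ANOVA on log change has 80% power. Example: s = 1.0 and ρ = 0.5 give SD = 1; a ratio of 1.47 gives d = ln 1.47 = 0.385 and λ = 100 × 0.667 × 0.148 = 9.9. ANOVA on raw change was then applied to the same simulated data (8,000 trials per cell, 100 per arm, range over ρ):

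| log-SD | log change | raw change | loss, points |
|---|---|---|---|
| 0.25 | 80% | 79-81% | about 0 |
| 0.5 | 80% | 74-77% | 3-6 |
| 0.75 | 80% | 64-71% | 9-16 |
| 1.0 | 80% | 52-62% | 18-28 |
| 1.25 | 80% | 38-51% | 29-42 |
| 1.5 | 80% | 29-41% | 39-51 |

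With 80 per arm (20% loss) the picture is the same: 52-64% at log-SD 1.0 and 31-42% at 1.5.

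**Step 4: type I error.** With no effect, the raw-change test rejected in about 3-6% of trials.

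**Step 5: scale and covariate separately.** For a 1.5-fold effect, log-SD 1.0 and ρ = 0.5, power over repeated runs was: raw change 61-63%; raw 12-month value with baseline as covariate 72-74%; log change 85%; log 12-month value with log baseline as covariate 93-95%. Both parts help.

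**Step 6: homebound weeks.** Some weeks may have almost no travel; eligibility in Protocol 2.2 requires impairment in daily activities. Assume a median of 5 km and homebound weeks independent of arm and time point.

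| Scenario | raw change | log with baseline covariate and low floor |
|---|---|---|
| log-SD 1.0, 1.5-fold, 5% homebound, 10 m floor | 58% | 36% |
| log-SD 0.5, 1.3-fold, 5% homebound, 10 m floor | 89% | 21% |
| log-SD 1.0, 1.5-fold, 10% homebound, 5 m / 50 m floor | 51-52% | 21% / 35% |

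The log turns these weeks into extreme low outliers. A 1 km floor restored 84% and 71% at log-SD 1.0 and 1.5-fold with 5% and 10% homebound. In one setting (log-SD 0.5, 10% homebound) it still fell below raw change: 69% against 76%.

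**Step 7: rank ANCOVA** (12-month rank on baseline rank and arm). It beat raw change in every effect scenario tried, with and without homebound weeks. At log-SD 1.0 and 1.5-fold it moved power from 58% to 80% with 5% homebound weeks, and from 51% to 67% with 10%.

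**The case against.** Mean change in meters is a legitimate target, and a rank or log analysis answers a different question. That stands as a real cost of the change. It does not remove the problem that, under strong skew, the mean change in meters is estimated with little precision.

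Every magnitude rests on assumed skewness, correlation and effect. This also stands: at log-SD 0.5 or less there is little to gain.

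A reader might infer that one traveller can produce a false positive. The point estimate can indeed be moved by a few people, but the error rate under no effect stays near 5%, so the documents and the calculation do not support a claim of inflated type I error.

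A reader might also infer that taking logs is always at least as good. That holds only when there are no near-zero weeks. With 2% homebound weeks, log-SD 0.5 and a 1.3-fold effect, raw change had 94% power, against 41% with a 5 m floor and 65% with a 50 m floor.

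Finally, this is one of nine secondary outcomes (five patient-reported, four GPS), in a subset that Protocol 10.1 describes as optional.

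**Conclusion.** The point holds as a conditional loss of power. If radius of gyration is roughly lognormal with log-SD of about 0.75 or more and the effect is proportional, the planned test gives up about 9 to 51 points against an 80% benchmark, depending on skew and correlation. At log-SD 0.5 the loss is about 3 to 6 points, and at 0.25 it is nil. The documents cannot show which case applies, because they give no spread. They do show that the plan has no protection if the skew is strong, although the baseline value that would help is already collected.

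Type I error is not at issue. The primary outcome, a T score, is untouched.

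**What to change.** In the SAP, replace the change-score ANOVA for this outcome with a comparison of 12-month radius of gyration between arms that uses the baseline value as covariate, by rank-based ANCOVA: 12-month rank on baseline rank and arm. Report medians in meters by arm.

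If a log scale is preferred, prespecify a floor well above device accuracy, add a sensitivity analysis over several floor values, and report geometric-mean ratios alongside the medians.

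The SAP is dated October 2023 and describes its analyses partly in the past tense. If results have already been seen, keep the planned ANOVA and label the new analysis as a sensitivity analysis.

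The cost is one or two sentences and no new data. The downside is that the test no longer targets the mean difference in meters, and a rank result has a less direct effect scale.

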We propose a 3-arm randomized clinical trial of 600 individuals with physical disabilities. Study participants will be randomly assigned to one of three conditions, each lasting 6 months: (1) The intervention (EW-D), (2) an attention control condition (8 sessions of wellness education, based on the CDC's "10 Keys to Healthy Aging" course), or (3) treatment as usual (TAU). Assessments will be conducted at baseline, 3 months, 7 months, and 12 months. We seek to evaluate the EW-D intervention to serve disabled individuals in middle-age. Our primary treatment target is satisfaction with community participation. We will also look at mediators of these effects, including disease management self-efficacy and resilience. Our intervention will be compared to the two control conditions – one based on educational materials and a second based in treatment-as-usual. Both self-report and GPS based data will be used to test the study hypotheses.

1.6 Study design. Provide a one-sentence description of the general study design and/or type of methodology.

Your answer will help HSD in assigning applications to reviewers and in managing workload. Examples: a longitudinal observational study; a double-blind, placebo-controlled randomized study; ethnographic interviews; web scraping from a convenience sample of blogs; medical record review; coordinating center for a multi-site study.

This is a randomized, controlled trial of an adapted wellness promotion intervention to be carried out in a large sample of middle-aged adults with long-term physical disabilities.

1.7 Intent. Check all the descriptors that apply to your activity. You must place an "X" in at least one box.

This question is essential for ensuring that your application is correctly reviewed. Please read each option carefully.

Descriptor
 1. Class project or other activity whose purpose is to provide an educational experience for the researcher (for example, to learn about the process or methods of doing research).
 2. Part of an institution, organization, or program's own internal operational monitoring.
 3. Improve the quality of service provided by a specific institution, organization, or program.

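### The SAP tests every outcome with an ANOVA on change scores and no baseline covariate, which is unbiased but less precise than adjusting for the baseline already collected

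*SAP*

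**What the plan says.** The SAP's Statistical Approach gives the whole inferential plan in a few sentences. "ANOVAs were used as an omnibus test to determine if there were any differences in the change scores between treatment groups", and this is done "for each of the primary and secondary outcomes". Pairwise comparisons follow: "If the omnibus test was significant, a post-hoc Tukey's honest significant difference tests were used to assess pairwise differences between treatment groups". The level is fixed too: "A two-sided significant level of 0.05 was used to determine if differences were statistically significant". No covariate, analysis of covariance or mixed model is named, and the protocol contains no analysis model that would supply one.

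The SAP lists ten outcomes: one primary, five patient-reported secondary and four GPS-based secondary. Each is defined as a change. Under Assessment timeline it states "Patient reported outcomes collected at baseline (pre-randomization), and at 3, 6 and 12 months post-randomization" and "GPS outcomes collected at baseline (pre-randomization) and at 12-month follow-up". Protocol 5.1 confirms that the baseline survey comes before randomization.

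Protocol 1.5 sets the comparison: "Our intervention will be compared to the two control conditions". The SAP's title block reads "Document Last Updated: October 26, 2023", and the description of the tests is in the past tense.

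**The concern.** A change score uses the baseline by subtraction. That fixes the slope of follow-up on baseline at 1, whatever the data show. A linear model with baseline as a covariate estimates the slope instead. If the true slope is below 1, as it is whenever the two visits have equal SDs and r is below 1, subtraction removes too much and adds baseline noise to the outcome.

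The trial has to separate EW-D from two controls, each at the stricter Tukey threshold. Avoidable variance lowers power and widens the interval for both contrasts. The GPS outcomes have the least room for this, because Protocol 5.1 plans only 100 participants per arm for them.

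**Working it through.** **Inputs from the documents.** 600 participants in three arms (Protocol 1.5 and 5.1); 300 in the GPS subset, 100 per arm (Protocol 5.1); two-sided 0.05 and Tukey after an omnibus test (SAP).

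**Assumptions.** The documents give no power statement, target difference, SD, correlation or allocation ratio, so there is no planned figure to reproduce. I take 200 per arm, r from 0.5 to 0.8, true differences of 0.20 to 0.30 SD, and complete follow-up.

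**Step 1: variance.** Let the outcome have variance 1 at both visits.

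- Change score: 2(1 − r).
- Follow-up adjusted for baseline: 1 − r².
- Ratio, adjusted to change: (1 − r²) / [2(1 − r)] = (1 + r)/2.

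Multiplying 600 by the ratio gives the number of participants who, analysed with adjustment, carry the same information as 600 analysed by change score.

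| r | ratio | equivalent N |
|---|---|---|
| 0.5 | 0.75 | 450 |
| 0.6 | 0.80 | 480 |
| 0.7 | 0.85 | 510 |
| 0.8 | 0.90 | 540 |

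**Step 2: unequal SDs.** If the follow-up SD is k times the baseline SD, the ratio is k²(1 − r²) / (1 + k² − 2rk).

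- k = 0.8: 0.57 at r = 0.5, rising to 0.64 at r = 0.8.
- k = 1.25: 0.89 at r = 0.5, rising to 1.00 at r = 0.8.

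The ratio reaches 1 only when the slope rk equals 1, as in the last case (0.8 × 1.25 = 1). In large samples it does not exceed 1.

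**Step 3: power per contrast.** The Tukey critical value for three groups is the 0.95 quantile of the studentized range divided by √2, which is 2.350. Power comes from the noncentral t with 597 df (change) or 596 df (adjusted), with noncentrality d / √(2 × variance / 200).

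Example with d = 0.25 and r = 0.5. For change the variance is 1.00, the standard error √(2 × 1.00/200) = 0.100 and the noncentrality 2.50. Adjusted, the variance is 0.75, the standard error 0.0866 and the noncentrality 2.89. Power is 56.0% and 70.4%.

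| r | 0.20 SD, change → adjusted | 0.25 SD | 0.30 SD |
|---|---|---|---|
| 0.5 | 36.4 → 48.4% | 56.0 → 70.4% | 74.2 → 86.7% |
| 0.6 | 45.5 → 56.0% | 67.2 → 78.1% | 84.2 → 91.9% |
| 0.7 | 59.2 → 67.4% | 81.0 → 87.5% | 93.6 → 96.8% |
| 0.8 | 79.2 → 83.7% | 94.5 → 96.5% | 99.2 → 99.6% |

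For the GPS subset (100 per arm, 0.25 SD) the same calculation gives 28.0 → 37.8% at r = 0.5 and about 67 → 72% at r = 0.8.

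**Step 4: simulation of the full procedure.** Omnibus F then Tukey, 20,000 trials per r, 200 per arm, EW-D 0.25 SD better than both controls. The mean estimate was 0.249 to 0.250 under both analyses, so neither is biased. Observed variance ratios were 0.753, 0.797, 0.860 and 0.899 against the theoretical 0.75, 0.80, 0.85 and 0.90. Power to show EW-D better than both controls rose from 39 to 56%, 52 to 66%, 70 to 79% and 90 to 94% at r = 0.5, 0.6, 0.7 and 0.8.

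**Step 5: the outcome definition.** Regressing follow-up minus baseline on arm and baseline gives the same arm coefficient as regressing follow-up on arm and baseline; only the baseline slope falls by 1. The outcomes can therefore stay defined as changes.

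**The case against.** The change-score ANOVA is a legitimate analysis. It matches outcomes defined as changes, it is unbiased under randomization with complete follow-up, and Tukey controls the pairwise error. All of that stands, and it is why this is a point of efficiency.

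The size is not tied to this trial. Every power figure depends on assumed inputs, the gain shrinks to almost nothing at high r with a large difference, and no documented power target is shown to be missed. That also stands. A strict gain on all ten outcomes is not guaranteed either: if follow-up is more variable than baseline and r is high, the ratio can reach 1. The careful statement is that adjustment is no less precise in large samples and usually more so. None of this gives a reason to prefer the change score.

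Two other gaps bear on both analyses equally. The SAP does not say which follow-up visit defines the change, and it states no missing-data method although Protocol 5.1 and 10.7 provide for withdrawing unreachable participants. Baseline adjustment among completers would not by itself cure differential dropout. These are separate points and do not answer this one.

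**Conclusion.** The concern holds. The plan leaves precision unused on the primary and secondary outcomes although the covariate is already collected. The direction is certain in large samples unless the slope of follow-up on baseline is exactly 1. The size depends on r and on the ratio of the SDs, which the documents do not give. With equal SDs the change-score analysis forgoes the equivalent of 25% of the sample at r = 0.5 and 10% at r = 0.8. The change should be made, but the planned test is not invalid without it.

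**What to change.** For each primary and secondary outcome, replace the change-score ANOVA with a linear model of the follow-up (or change) score on arm plus the baseline value of the same outcome. Take the omnibus test of arm from that model, and apply the Tukey-adjusted pairwise comparisons to the adjusted means. The model statement has to name the follow-up visit for each outcome, since the patient-reported outcomes have three.

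The SAP should also state whether outcomes by arm had been seen when it was written; its date and past tense leave this open. If they had not, the change is one of SAP wording. If they had, keep the change-score ANOVA as specified and report the baseline-adjusted model beside it as a labelled sensitivity analysis, which costs one added table. Either way no new data are needed and each model spends one degree of freedom (597 to 596 with 600 participants).

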2 PARTICIPANTS

2.1 Participants.

Describe the general characteristics of the subject populations or groups, including age range, gender, health status, and any other relevant characteristics.

Participants will be adults with long-term physical disabilities age 45-64 years. We plan to recruit participants representing different genders and racial backgrounds. Our goal is to complete data collection with 600 participants; however, we will request approval for 750 participants in case of incomplete initial sessions/surveys, no shows, or withdrawals. Before initiating the intervention study, up to 10 pilot participants will provide feedback some of this study's procedures and materials.

Since this specific trial is looking at evaluating the effectiveness of the EW-D intervention in middle-aged adults with disabilities, the inclusion criteria includes only adults 45 to 64 years of age.

Neither the EW-D intervention nor the CDC educational materials are available in languages other than English. This study seeks to test the effectiveness of the EW-D intervention as it is currently developed in English; future studies should look at the effectiveness of the intervention translated into other languages.

2.2 Inclusion and exclusion criteria.

Describe the specific criteria you will use to decide who will be included in your study from among interested or potential subjects. Define any technical terms in lay language.

The inclusion exclusion criteria for all participants (except for pilot participants where noted) are as follows:

Inclusion Criteria:

- 45 to 64 years of age at screening (turning 65 years after screening is ok);
- Able to read, write and understand English;
- Has a self-reported physical diagnosis of a medical condition affecting the muscular and/or neurologic systems (eg, muscular dystrophy, multiple sclerosis, post-polio syndrome, spinal cord injury, limb loss, prosthetic users, etc.), and the condition:
 - creates functional disability (impairment in ADL OR IADL)
 - symptom onset before age 40 years (main study only, not required for pilot participants)
- Able to participate via telephone or Zoom;
- Has a goal in mind if randomized to the EW-D intervention (main study only, not required for pilot participants);
- Has not participated in the original EnhanceWellness intervention group (main study only, not required for pilot participants).

Exclusion Criteria:

- Unable to read, write or understand English;

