Pilot data have shown that participation in EnhanceWellness for middle-aged adults with long-term physical disability has a variety of positive impacts, including greater satisfaction with social roles and activities, self-efficacy for disability management, and decreases in pain interference and fatigue. Although we do not anticipate that the education control condition will result in any improvements in the outcome variables studied, previous participants report high levels of satisfaction with educational materials, and report that they find the information useful. There is a benefit to others, in that demonstrating the efficacy of this intervention may improve access to health/wellness promotion interventions for people with long-term physical disabilities. There is otherwise no direct benefit of participation in this research.

10.9 Individual subjects findings.

a. Is it likely that your research will unintentionally discover a previously unknown condition such as a disease, suicidal intentions, or genetic predisposition?

No
 Yes

→ If yes, explain whether and how you would share the information with the subject.

It is possible that we may learn of suicidal ideation from participants during their conversations with the Wellness Coach/social worker or other study personnel. We will follow a suicide ideation (SI) protocol should this occur (**Appendix 20**), though we do not believe any study procedures will directly cause suicidal ideation. If a participant reveals thoughts of suicide, study personnel will follow all of the steps outlined in the SI protocol.

b. Do you plan to routinely share the individual results of your study procedures with the subjects – such as genetic test results, laboratory tests, etc.?

No
 Yes

→ If yes, complete and upload the [SUPPLEMENT: Participant Results Sharing](#) to the [Supporting Documents](#) SmartForm of **Zipline**

10.10 Commercial products or patents. If a commercial product or patent could result from this study, describe whether subjects might receive any remuneration/compensation and, if yes, how the amount will be determined:

n/a

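### With three arms, the omnibus F test already protects ordinary pairwise t tests, so using Tukey's critical value behind it costs power that error control does not require

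*SAP*

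**What the plan says.** The SAP's Statistical Approach sets the testing rule for the primary and every secondary outcome. First, "ANOVAs were used as an omnibus test to determine if there were any differences in the change scores between treatment groups". Then, "If the omnibus test was significant, a post-hoc Tukey's honest significant difference tests were used". The level is fixed by "A two-sided significant level of 0.05 was used to determine if differences were statistically significant". As its reason for needing nothing more, the SAP adds that "Tukey's HSD test inherently controls the type I error rate for the pairwise comparisons".

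The Protocol gives the context. Section 1.5: "We propose a 3-arm randomized clinical trial of 600 individuals with physical disabilities", and "Our intervention will be compared to the two control conditions". Section 2.1: "Our goal is to complete data collection with 600 participants". On the expected pattern of means, section 10.8 says "Although we do not anticipate that the education control condition will result in any improvements in the outcome variables studied".

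Neither document states an effect size, a standard deviation, a target power or an allocation ratio.

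**The concern.** A pairwise claim has to pass two tests, each of which controls the family-wise error alone when there are three arms. The SAP's own rationale credits Tukey with the control, which leaves the gate with no stated job. Conversely, once the gate is there, three arms need nothing stricter than ordinary t tests behind it.

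At stake is efficiency, not validity. The trial's question is EW-D against education and EW-D against TAU. The rule makes both contrasts harder to show than a 5% family-wise error demands, and the loss is largest where the trial would most like to succeed, on both together.

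**Working it through.** **Inputs.** From the documents: three arms, 600 participants, two-sided 0.05, F test then Tukey. Assumed: equal allocation (200 per arm), normal change scores with a common SD, and effects of 0.20 to 0.40 SD. The main pattern of means is (d, 0, 0), with the two controls equal. Section 10.8 of the Protocol supports that pattern, since it expects no improvement from education. There is no power figure in the plan to reproduce.

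**Why F then t is enough with three arms.** The pairwise hypotheses are A=B, A=C and B=C. Any two of them together imply that all three means are equal, so the only intersection hypothesis is the global null, which the F test covers at 5%.
- All means equal: a false claim requires a false F rejection, so the error is at most 5%.
- Exactly one pair equal: only that pair can be a false positive, and its t test holds it at 5%.
- No pair equal: no false rejection of equality is possible.

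This argument is specific to three groups. Because 2.35 exceeds 1.96 and the gate is the same, F-then-t rejects whenever the SAP rule does.

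**Critical values** (df = 600 − 3 = 597). Ordinary t: 1.964. Tukey, as studentized range/√2: 2.350, a per-comparison level of 0.0191.

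**Hand check at d = 0.3, 200 per arm.** The standardized difference is 0.3/√(2/200) = 3.0.
- Ungated t test: Φ(3.0 − 1.964) = Φ(1.036) ≈ 85%.
- Tukey without the gate: Φ(3.0 − 2.350) = Φ(0.650) ≈ 74.2%.

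Adding the gate needs simulation (400,000 trials per scenario; repeat runs agree within about 0.2 points).

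**Family-wise error with all means equal.**

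| Rule | Error |
|---|---|
| Ungated t tests | 12.2% |
| Tukey alone | 5.0% |
| F then t | 5.0% |
| F then Tukey (SAP) | 4.5% |

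With means (0.3, 0.3, 0), the false-positive rate on the one truly equal pair under F then t is 5.0%.

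**Power, means (0.3, 0, 0), 200 per arm.**

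| Rule | Each EW-D contrast | Both contrasts |
|---|---|---|
| F then Tukey (SAP) | 73.9% | 61.1% |
| F then t | 81.7% | 75.3% |

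The differences are 81.7 − 73.9 = 7.8 points per contrast and 75.3 − 61.1 = 14.2 points for both. Tukey without the gate gives 74.2% per contrast, so the gate itself costs 74.2 − 73.9 = 0.3 points.

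**Sensitivity to effect size** (200 per arm, equal controls; loss per contrast against F then t):

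| d (SD) | 0.20 | 0.25 | 0.28 | 0.30 | 0.325 | 0.35 | 0.40 |
|---|---|---|---|---|---|---|---|
| Loss (points) | 7.7 | 9.0 | 8.5 | 7.8 | 6.5 | 5.1 | 2.5 |

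With 160 per arm (an assumed attrition case) the loss is 8.9 points at 0.30 and 4.7 at 0.40.

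**Sensitivity to the pattern of means.** If education has half the effect, (0.28, 0.14, 0), the loss is 69.5 − 66.1 = 3.4 points for EW-D against TAU. For EW-D against education it is about 10 points (27.5% against 17.1%). In this graded pattern, dropping only the gate recovers at most about 1.5 points.

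**The case against.** The strongest reply is that F then Tukey is a familiar, valid rule, that the SAP says openly why Tukey was chosen, and that the documents state no power target it would miss. All of that is true, and it makes this an efficiency point only.

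Three technical limits also stand.
- **Equal variances.** The 5% guarantee for F then t relies on them. As an assumed illustration, take arm sizes of 160/200/200, SDs of 1.3/1/1 and one truly null pair between the smaller and a larger arm. The error on that pair is 6.8% with F then t and 2.9% with Tukey. The GPS outcomes (trips, metres, minutes) are where equal variance is least certain.
- **Scope of control.** The guarantee is per outcome and per time point. The SAP lists 3, 6 and 12 months and names no primary time point; neither rule controls error across them.
- **Intervals.** Ordinary pairwise intervals are not simultaneous. If Tukey intervals are shown beside F-gated t tests, a difference declared significant can have an interval that includes zero, in about 8% of trials per contrast at 0.3 SD. The present rule has a small mismatch too, since a Tukey interval can exclude zero when the gate fails.

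The gain also depends on how success is defined. Power to show at least one pairwise difference at (0.3, 0, 0) moves only from 86.8% to 88.2%.

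A reader might infer that requiring both tests is what costs 8 points, so that removing either layer would repair it. The figures do not support that: the gate on top of Tukey costs almost nothing, and the loss comes from Tukey's critical value behind the gate. A reader might also infer a fixed loss of 8 points on every key contrast. That needs an effect size the documents do not give, and controls that are truly equal.

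**Conclusion.** The point holds as one of efficiency. The SAP's rule is valid and slightly conservative, and in a three-arm trial under a pooled equal-variance model Tukey behind a significant F test adds a penalty that 5% family-wise control does not need. The comparator for the loss is F-gated t tests. Against it, the plan gives up about 8 points per EW-D contrast and about 14 points for both, at 200 per arm, 0.3 SD and equal controls. The per-contrast loss ranges from about 2.5 to 9 points over 0.20 to 0.40 SD, and it is unequal, about 3 points against TAU and 10 against education, if education works partly. Nothing here suggests inflated error or an invalid analysis.

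**What to change.** Replace the sentence on Tukey, and the sentence giving Tukey as the source of error control, with:

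> If the omnibus test is significant at 0.05, each pairwise difference is tested with the model-based t test at two-sided 0.05; with three arms this closed procedure holds the family-wise error at 5% for each outcome and time point.

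Removing the gate and keeping Tukey is not an equivalent alternative.

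The edit needs no participants or data. The SAP should state its costs: the pairwise intervals are not simultaneous, any Tukey intervals shown alongside may include zero for a difference declared significant, and the guarantee assumes roughly equal variances.

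Timing matters. The Statistical Approach is largely in the past tense and the SAP was last updated on October 26, 2023, so the analysis may already have been run, although the documents do not say so. If arm-level results have been seen, keep the existing rule as primary and report F then t as a labelled sensitivity analysis, because lowering the critical value at that stage would be a post hoc relaxation.
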